Allogeneic HB-adMSCs to provide immune support against COVID-19.

Study Endpoints

Primary endpoints:

- Incidence of hospitalization for COVID-19.
- Incidence of symptoms associated with COVID-19.

Secondary endpoints:

- Absence of upper/lower respiratory infections (with hospitalization criteria) up to 3 months post infusions.
- Change from baseline in leukocyte differential
- Change from baseline in C-Reactive Protein
- Change from baseline in TNF-alpha
- Change from baseline in IL-6
- Change from baseline in IL-10
- Clinically significant changes in laboratory values, vital signs, weight, X-rays, ECG, and physical examination results.
- Incidence of AEs (AEs) and serious AEs (SAEs) related to the drug

Investigational Plan

This Phase 2, randomized, double-blind, single center, efficacy and safety study, is designed to evaluate allogeneic HB-adMSCs to provide immune support against COVID-19 in subjects classified as high risk. 'High risk', according to CDC at the time of protocol development, includes subjects age 65 or older, as well as subjects in high exposure environments such as healthcare professionals and law enforcement, or individuals with preexisting conditions, including but not limited to cardiopathies, diabetes mellitus, cancer, COPD, asthma or any other systemic autoimmune disease. The study will have 4 arms:

Arm 1 (allogeneic HB-adMSCs 200MM)

Subjects assigned to this arm will receive HB-adMSCs during the whole duration of the study.

Arm 2 (allogeneic HB-adMSCs 100MM)

Subjects assigned to this arm will receive HB-adMSCs during the whole duration of the study.

Arm 3 (allogeneic HB-adMSCs 50MM)

Subjects assigned to this arm will receive HB-adMSCs during the whole duration of the study.

Arm 4 (Placebo)

Subjects assigned to this arm will receive placebo injections throughout the entire duration of the study.

The screening period, up to 45 days long for each patient, will be used to assess eligibility. At baseline (Week 0), approximately 53 patients who are eligible will be randomized in a 3:1 ratio

Allogeneic HB-adMSCs to provide immune support against COVID-19.

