Allogeneic HB-adMSCs to provide immune support against COVID-19.

- The patient develops a severe allergic reaction that occurs following investigational product administration.

A patient may voluntarily withdraw or be withdrawn from the study at any time for reasons including, but not limited to, the following:

- Patient withdrawal of consent: At any time, a patient's participation in the study may terminate at his/her request. The specific reason for patient withdrawal will be noted on the case report form (CRF).
- Lost to follow-up: The patient stops coming for visits, and study personnel is unable to contact the patient after repeated attempts (e.g., mail, or email).
- This study may be terminated at the discretion of the Sponsor or any regulatory agency.

If a patient's infusions are discontinued at any point during the trial and the patient maintains consent to contribute additional outcome information, the patient should continue to be followed through Week 26 for all safety and efficacy assessments. Investigators will be trained about the importance of retention and steps to prevent missing data.

The date and reason for withdrawal are to be documented in the CRF. The study site must immediately notify the medical monitor. The patients who withdraw prematurely must attend an early discontinuation visit if possible, at which time they will complete all assessments described in Table 2 under the Week 24 visit.

In the event that a patient discontinues prematurely from the study due to an Adverse Event (AE) or serious AE, the event will be followed until it resolves (returns to normal or baseline values) or stabilizes, or until it is judged by the Investigator to be no longer clinically significant. Once a patient is withdrawn from the study, the patient may not re-enter the study. If the subject develops symptoms associated with COVID-19 during the conduct of this study, they will be asked to consult their personal physician and be tested for COVID-19, and to self-quarantine for at least 14 days. Quarantine must occur while waiting for COVID-19 test results. Once asymptomatic, subject may resume site visits. If the test results are positive, the subject will be asked to quarantine and may continue to receive infusions at the quarantine site. If the subject develops severe symptoms (i.e., shortness of breath/difficulty breathing) they should go to the ER instead of personal physician.

Treatments

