It is the responsibility of the Principal Investigator to oversee the safety of the study at his/her site. This safety monitoring will include careful assessment and appropriate reporting of adverse events as noted above. At Hope Biosciences, [name], MD [contact] will be responsible for reviewing any reported AEs and SAEs to determine if changes to the study need to be made or if the study should be stopped for the protection of patients. DSMB will review all deaths (to assure non-attribution), cases of anaphylaxis or suspected anaphylaxis, thromboembolic events, new malignancy/tumor, infections/hospitalizations (including unrelated to COVID-19 but due to underlying condition). After 15 subjects diagnosed with COVID-19, 5 subjects are hospitalized, or 3 subjects in the ICU, DSMB will review. DSMB will also review safety data at mid-point of the study.

Risks

Potential Risks of the Investigational Product and Clinical Investigation

Risks Associated with HB-adMSCs

Respiratory Risks:

A potential risk is that the infusion could initiate a VTE event with subsequent cardiopulmonary sequelae of respiratory failure and/or right heart strain/failure. We plan to monitor oxygen saturation, and respiratory rate/work of breathing for the first 2 hours post- infusion. The patient will be examined for VTE events (clinical exam, oxygen saturation) during each infusion visit and at each follow-up visit.

Hepatic Risks:

The reticuloendothelial system can sequester immature blood elements, theoretically resulting in hepatic injury. An acute elevation of the AST/ALT hepatic enzymes > 900 U/dl post-infusions will be considered an infusion related adverse event. This level is based upon the organ system scoring definitions for moderate hepatic failure and corresponds to the CTCAE v4.03 Grade 4 adverse event. It is unlikely that "end vessel" micro-thrombosis would occur in the liver due to the dual blood supply of the liver and the lung is the first pass organ. A CMP will be obtained at follow-up visits.

Coagulation Cascade:

A coagulation panel will be obtained at screening, baseline, infusion and the follow-up visits. The patient will be monitored for the development of venous thromboembolic events (see pulmonary monitoring above) as well as for the development of clinical deep vein thrombosis (limb swelling, tenderness, discoloration).

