4. ANALYSIS POPULATIONS

Population	Definition / Criteria	Analyses Evaluated
Safety analysis set	
• All randomised subjects who received at least one dose of HB-adMSCs infusion or placebo.• If participants receive a treatment different to their randomized treatment, they will be analysed according to the treatment actually received.	
• Safety• Study Population
Efficacy analysis set	
• All randomized participants who received all 5 infusions of HB-adMSCs or placebo.• Participants will be analysed according to their randomized treatment.	
• Efficacy

Protocol Number: HBCOVID02
 Hope Biosciences
 Statistical Analysis Plan

Confidential

Date: 14-Oct-2021
 Version: 1.0
 Status: Final

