7. EFFICACY ANALYSES

7.1. Primary Efficacy Analyses

7.1.1. Endpoint / Variables

The primary endpoints are incidence of COVID-19 symptoms and Hospitalizations due to COVID-19 symptoms after Week 26 end of study.

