7.1.2. Summary Measure

Binomial proportions difference between treatments.

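### The severe-outcome primary endpoint counts COVID-19 hospitalization but not death, so a COVID-19 death without admission is never counted as a failure on it

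*Protocol*

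**What the plan says.** The protocol (Study Endpoints, repeated in the Synopsis) names two primary endpoints: "Incidence of hospitalization for COVID-19" and "Incidence of symptoms associated with COVID-19". SAP 7.1.1 restates them: "The primary endpoints are incidence of COVID-19 symptoms and Hospitalizations due to COVID-19 symptoms after Week 26 end of study". The effect measure in SAP 7.1.2 is "Binomial proportions difference between treatments".

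SAP 7.1.3 bases the primary analysis on the efficacy set, which SAP section 4 defines as "All randomized participants who received all 5 infusions of HB-adMSCs or placebo". The protocol's Analysis Population section also requires five infusions. The fifth is scheduled at Week 14, and follow-up ends at Week 26.

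Death appears only on the safety side: as a criterion for a serious adverse event, in the study stopping rules, and under Medical Monitoring, where the "DSMB will review all deaths (to assure non-attribution" among other events. Neither document has a composite with death, a competing-event method, or a rule for scoring a subject who dies. LOCF is mentioned in SAP 5.5 only for plots. Hospitalization is not defined.

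In the protocol's Withdrawal, Removal, and Replacement section, subjects with severe symptoms are told that "they should go to the ER instead of personal physician". A subject is lost to follow-up when staff are "unable to contact the patient after repeated attempts (e.g., mail, or email".

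**The concern.** An endpoint meant to capture severe COVID-19 should count the most severe outcome. As written, it counts a fatal case only if an admission came first. Test-positive subjects quarantine outside hospital, and the protocol treats emergency care as something that can occur without hospitalization. Death without admission is therefore possible under the plan, if unlikely. The protocol's Risks section also lists worsening of COVID-19 as a potential risk of the product. An uncounted death on active treatment would flatter the product, and one on placebo would understate any benefit. With about 13 placebo subjects, a single case carries weight.

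**Working it through.** **1. What happens to a COVID-19 death without admission.** With a binomial outcome, every analysed subject is an event or a non-event.

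- *After the fifth infusion* (about Weeks 14 to 26, 12/26 = 46% of the follow-up period): the subject is in the efficacy set and has no hospitalization, so is a non-event. This is inferred from the definition; no rule states it. The symptom endpoint would normally count the subject, if the preceding fever, cough or breathlessness was recorded.
- *Before the fifth infusion*: the subject cannot have had five infusions, so drops out of both primary analyses and remains only in the safety reporting.
- *After a COVID-19 admission, among subjects in the efficacy set*: already counted.

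**2. How often.** The documents give no infection or fatality rate, so these are assumptions: 10-40% infected over the study, and 0.1-1% fatality among the infected.

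- Low: 53 × 0.10 × 0.001 = 0.005 expected deaths.
- High: 53 × 0.40 × 0.01 = 0.21 expected deaths.
- Chance of at least one at the high end (risk 0.40 × 0.01 = 0.004 per subject): 1 − 0.996^53 = 0.19.

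These count all COVID-19 deaths. Those without admission are a subset, so the relevant figures are lower.

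**3. What one case does.** The 3:1 allocation of 53 gives 53 × 0.75 = 39.75 and 53 × 0.25 = 13.25, about 40 and 13. The test is the pooled two-sample proportion test, two-sided at 0.05:

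z = (a/n − b/m) / √[p(1 − p)(1/n + 1/m)], with p = (a + b)/(n + m).

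- 0/40 vs 2/13: p = 2/53 = 0.0377, SE = 0.0608, z = −0.1538/0.0608 = −2.53, p-value 0.011.
- 1/40 vs 2/13: p = 3/53 = 0.0566, SE = 0.0738, z = −0.1288/0.0738 = −1.75, p-value 0.081.
- 0/40 vs 1/13: p = 1/53 = 0.0189, SE = 0.0434, z = −0.0769/0.0434 = −1.77, p-value 0.077.

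The event counts below are invented for illustration.

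| Death without admission | Not counted | Counted |
|---|---|---|
| One on active; 2 placebo hospitalizations | 0/40 vs 2/13, p = 0.011 | 1/40 vs 2/13, p = 0.081 |
| One on placebo; 1 placebo hospitalization | 0/40 vs 1/13, p = 0.077 | 0/40 vs 2/13, p = 0.011 |
| One on placebo; 2 placebo hospitalizations | 0/40 vs 2/13, p = 0.011 | 0/40 vs 3/13, p = 0.002 |

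Exclusion and non-event scoring give almost the same answer: dropping the active-arm death gives 0/39 vs 2/13, p = 0.012. After 15% drop-out (40 × 0.85 = 34; 13 × 0.85 = 11), the first row becomes 0.011 and 0.078. One subject is 100/40 = 2.5 percentage points on active and 100/13 = 7.7 on placebo.

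**4. Where one case does not change the conclusion.**

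- Fisher's exact test: 0.057 against 0.145 in the first row, and 13/53 = 0.245 against 0.057 in the second. Neither row crosses 0.05.
- One dose against placebo at 13 vs 13: 0 vs 2 gives 0.14, and 1 vs 2 gives 0.54. Neither is significant.

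**The case against.** The strongest reply is that the death would not be hidden. A late fatal case would normally be an event on the symptom endpoint and in the time-to-first-symptom analysis. Any death is a serious adverse event, reported within 24 hours, tabulated and reviewed by the DSMB. This stands, and it rules out the inference that the trial as a whole would score the worst outcome as a success. It does not repair the endpoint itself. The symptom endpoint weighs a fatal case like a cough, SAE tables are descriptive, and a death before the fifth infusion is missing from both primary analyses.

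Second, the event is improbable, and the p-value shifts depend on chosen counts and on the test. This stands too, and it sets the severity.

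Three stronger readings are tempting but unsupported:

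- *Every such death is scored as not hospitalized.* Earlier deaths are excluded, not scored.
- *The same subject would count as free of respiratory infection on the secondary endpoint.* That depends on its reference to hospitalization criteria, which is undefined. The Synopsis objective speaks of infections that require hospitalization, and a fatal emergency case could be read as meeting that.
- *Follow-up relies on mail and email alone.* These are given as examples, and the schedule includes telephone calls around each infusion.

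**Conclusion.** The concern holds as a minor point. The severe-outcome primary endpoint omits death, and the five-infusion set removes early deaths, so no COVID-19 death without admission counts as a failure on it. The bias can go either way, depending on the arm. At most about 0.2 COVID-19 deaths of any kind are expected in 53 subjects, under assumed infection and fatality rates that the documents do not supply. One such death can move the pooled comparison across 0.05 (0.011 to 0.081, or 0.077 to 0.011), but only at particular event counts and with the pooled proportion test at about 40 vs 13. A reader might infer that harm would be concealed. The documents do not support that, because safety reporting would show the death.

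**What to change.** - **Endpoint.** Define it as hospitalization for COVID-19 or death from COVID-19. Change the protocol Synopsis, Study Endpoints and the Endpoints part of Statistical Analysis, and SAP 2.1, 2.3, 5.4, 7.1.1 and 7.1.4.1, with the matching sentences in SAP 5.5 and 6.1.
- **Analysis set.** Analyse this endpoint in all randomized subjects who received at least one infusion, by randomized arm. Amend the protocol's Analysis Population section and SAP 4, 5.5 and 7.1.3. Without this, the new definition still loses deaths before the fifth infusion.
- **Secondary respiratory endpoint.** Count death from a respiratory infection as failure.
- **Minor addition.** Before classing a subject as lost to follow-up, try by telephone as well and record vital and hospital status.

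Cost: wording in both documents, a different analysis set for this endpoint, and attribution of the cause of each death, preferably blinded to arm. No extra subjects or visits are needed.

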Unblinding of patient and researcher will occur in the case of adverse event suspected to be related to the investigational product, per the medical monitor and DSMB.

Regulatory authorities and/or the IRB may request the unblinding of data from one or more patients at any time.

Prior and concomitant conditions

The investigators should document all prior significant medical history. Additional conditions present at the time when informed consent is given and up to the time of first infusion (Week 0) are to be regarded as concomitant conditions. Illnesses first occurring or detected during the study and/or worsening of a concomitant condition during the study should be documented as AEs in the CRF.

Prior and concomitant medications

All medications, including over-the-counter treatments and preventative vaccines taken by the patient during the study, including those treatments initiated prior to the start of the study, must be recorded in the CRF. The entry must include the dose, regimen, route, indication, and dates of use.

Study Procedures

Table 2 outlines the timing of procedures, and assessments to be performed throughout the study.

Table 2. Schedule of Assessments

Visit Number	1	2	3	4	5	6	7	8	9
Weeks	N/A	Week 0	Week 2	Week 6	Week 10	Week 14	Week 18	Week 22	Week 26
Visit Name	Screening (Phone call)	Infusion-1 /Baseline	Infusion 2	Infusion 3	Infusion 4	Infusion 5	Follow Up	Follow Up	EOS
Window Period	Up to 45 days	±4 days	±4 days	±4 days	±4 days	±4 days	±4 days	±3 days	±3 days
STUDY PROCEDURES									
Informed Consent	X	X							
Inclusion and Exclusion Criteria	X	X							
Pre-infusion assessment		X	X	X	X	X			
Review of Medical History	X	X	X	X	X	X	X	X	X
Concomitant Medication Review	X	X	X	X	X	X	X	X	X

Allogeneic HB-adMSCs to provide immune support against COVID-19.

Vital Signs		X	X	X	X	X	X	X	X
Weight and Height ¹		X	X	X	X	X	X	X	X
Physical Examination		X	X	X	X	X	X	X	X
SF-36 Questionnaire		X	X	X	X	X	X	X	X
PHQ-9		X	X	X	X	X	X	X	X
Rapid antibody COVID-19		X							X
CBC with differential		X		X		X			X
Chemistry		X		X		X			X
Coagulation Panel		X		X		X			X
CRP		X		X		X			X
IL-6		X		X		X			X
IL-10		X		X		X			X
TNF alpha		X		X		X			X
HB-adMSCs Administration		X	X	X	X	X			
24-hour telephone encounter		X	X	X	X	X			
Adverse Event Monitoring		X	X	X	X	X	X	X	X
1. Height will only be measured at baseline									

Informed Consent (ICF)

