Subjects may benefit from their participation in the study by experiencing an overall feeling of well-being. Subjects enrolled in the study will be contributing to the advancement of science and to future investigations regarding stem cells and possible therapeutic applications, including treatment and prevention of respiratory diseases, specifically COVID-19.

Statistical Analysis

Determination of Sample Size

Sample size calculation was determined based upon the number of patients currently banked at our facility and those who are already registered to bank. Sample size for this study is not to exceed 53 patients.

Null hypothesis- Efficacy

Treatment with HB-adMSCs does not cause changes in primary and secondary endpoints (listed below) for providing immune support against Coronavirus Disease.

Alternative hypothesis-Efficacy

The alternative hypothesis for this study is that HB-adMSCs treatment does result in changes from baseline values of primary and secondary endpoints in patients.

Null hypothesis-Safety

Treatment with HB-adMSCs results in adverse or serious adverse events and/or detrimental changes in laboratory values, vital signs, weight, X-rays, ECG, or physical examination determined to be related to the study drug.

Alternative hypothesis-Safety

HB-adMSCs treatment for COVID-19 does not result in adverse or serious adverse events and/or detrimental changes in laboratory values, vital signs, weight, X-rays, ECG, or physical examination determined to be related to the study drug.

Endpoints

The endpoints measured in this study are safety and clinical efficacy.

Safety is assessed by incidence of adverse and serious adverse events, incidence of specific adverse events including serious infections, infusion-related reactions, hepatotoxicity, heart failure, and cytopenia. Clinically significant changes in laboratory values, vital signs, weight, and physical examination results will also be measured.

Allogeneic HB-adMSCs to provide immune support against COVID-19.

Clinical efficacy is assessed by primary and secondary endpoints. Primary endpoints include incidence of hospitalization for COVID-19, incidence of symptoms associated with COVID-19, and severity of symptoms associated with COVID-19. Secondary endpoints include absence of upper/lower respiratory tract infections, change from baseline in inflammation, SF-36 and PHQ9 questionnaires.

Analysis Population

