2. SUMMARY OF KEY PROTOCOL INFORMATION

2.1. Study Objective(s) and Endpoint(s)

Objectives	Endpoints
Primary Objective	Primary Endpoint

 To investigate the efficacy of HB-adMSCs in providing immune support against development of Coronavirus Disease by incidence of hospitalization for COVID-19, incidence of symptoms associated with COVID-19 (ie., fever, shortness of breath/difficulty breathing, and/or cough), and severity of COVID-19 associated symptoms (fever 38C or higher, cough, shortness of breath/difficulty breathing). 	
 Incidence of hospitalization for COVID-19. Incidence of symptoms associated with COVID-19
Secondary Objectives	Secondary Endpoints

 To investigate the efficacy of HB-adMSCs in the prevention of upper and lower respiratory infections in a high-risk population. 	
 Absence of upper/lower respiratory infections (with hospitalization criteria) up to 3 months post infusions. Change from baseline in leukocyte differential Change from baseline in C-Reactive Protein Change from baseline in TNF-alpha Change from baseline in IL-6 Change from baseline in IL-10 Clinically significant changes in laboratory values, vital signs, weight and physical examination results. Incidence of AEs (AEs) and serious AEs (SAEs) related to the drug

Protocol Number: HBCOVID02
 Hope Biosciences
 Statistical Analysis Plan

Confidential

Date: 14-Oct-2021
 Version: 1.0
 Status: Final

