8.2. Clinical Laboratory Analyses

Laboratory evaluations including the analyses of Biochemistry laboratory tests, Hematology laboratory tests and Coagulation tests (PTT/PT/INR). The details of the planned displays are in Appendix 5: List of Data Displays.

All laboratory parameters, including numerical urine analysis parameters will be summarised descriptively. Also, p-value for treatment difference using Analysis of variance (ANOVA) is displayed for lab parameters. Categorical urine analysis results will be summarized using count and percentage based on subjects.

Change from baseline will be summarised descriptively. Also, p-value for treatment difference using one-way Analysis of variance (ANOVA) is displayed for change from baseline.

Individual laboratory evaluations will be listed.

Data recorded at unscheduled assessments will not be included in tables and figures but will be listed.

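### X-rays and ECG are named in a secondary safety endpoint but never scheduled or analysed, and the SAP text plans no per-arm count of clinically significant laboratory changes

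*Protocol*

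**What the plan says.** The Study Endpoints section of the protocol lists, among the secondary endpoints, "Clinically significant changes in laboratory values, vital signs, weight, X-rays, ECG, and physical examination results". The null and alternative safety hypotheses under Statistical Analysis both refer to "detrimental changes in laboratory values, vital signs, weight, X-rays, ECG, or physical examination determined to be related to the study drug".

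Other statements of the endpoint are narrower. The Endpoints text in the same statistical section reads "Clinically significant changes in laboratory values, vital signs, weight, and physical examination results will also be measured". SAP 2.1 reads "Clinically significant changes in laboratory values, vital signs, weight and physical examination results", and the synopsis agrees with it.

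On data collection, the protocol says that "Table 2 outlines the timing of procedures, and assessments to be performed throughout the study". That table has no X-ray, ECG or urinalysis row.

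On analysis, SAP 8.2 says "All laboratory parameters, including numerical urine analysis parameters will be summarised descriptively" and adds that a "p-value for treatment difference using Analysis of variance (ANOVA) is displayed for lab parameters"; it plans a one-way ANOVA p-value for change from baseline as well. Individual laboratory values are listed. Unscheduled values go into listings but not into tables or figures.

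**The concern.** There are two separate problems.

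First, the endpoint and the hypotheses name assessments that the trial does not schedule. The alternative safety hypothesis is one of no drug-related harm, and it covers X-rays and ECG. If that wording stands, a report could appear to address both with no data behind it.

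Second, whether a change is clinically significant is a judgement about an individual patient. The protocol already asks the investigator to make it on every laboratory report. The laboratory analysis in SAP 8.2 does not use that judgement: it summarises distributions and tests differences in means. The harms that the protocol itself anticipates (hepatic injury, coagulation disturbance, cytopenia) could affect only one or two patients in a trial of 53. A non-significant ANOVA p-value printed beside such a case would look reassuring when it carries almost no information about it.

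**Working it through.** **Step 1: X-rays, ECG and urinalysis across the documents.**

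| Place | X-rays and ECG | Urinalysis |
|---|---|---|
| Protocol, Study Endpoints | named | no |
| Protocol, null and alternative safety hypotheses | named | no |
| Protocol, synopsis endpoints | absent | no |
| Protocol, Endpoints text in Statistical Analysis | absent | no |
| Protocol, Table 2 | no row | no row |
| Protocol, Assessments by Week | absent | absent |
| Protocol, Safety Assessments and laboratory test list | absent | absent |
| SAP 2.1 | absent | absent |
| SAP section 8 | absent | planned in 8.2 |

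X-rays and ECG are therefore promised in two places and collected in none. Urinalysis is planned for analysis and collected nowhere.

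**Step 2: what the SAP text provides for laboratory values.**

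- Descriptive summaries. SAP 5.5 defines these as N, mean, SE, SD, median, minimum and maximum.
- ANOVA p-values for values and for change from baseline.
- Listings of every value.
- Through SAP 8.1, AE tables giving the number and percentage of subjects. The protocol (Clinical Laboratory Parameters; Case Report Forms) requires results judged clinically significant to be recorded as AEs.

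The text contains no definition of a clinically significant change, no per-arm count of subjects with a flagged laboratory change, and no shift or out-of-range table. Appendix 5, the list of displays, was not available.

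**Step 3: what the ANOVA can detect.** The plan states no figure of its own here to reproduce. The protocol caps enrolment at 53, and 53 / 4 = 13.25, so assume four equal arms of 13. Let k patients in one arm have a change X and all other patients 0.

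- Affected arm mean: m = kX/13. The other arm means are 0 and the grand mean is m/4.
- SSB = 13 × [(3m/4)² + 3 × (m/4)²] = 0.75 × 13 × (kX/13)²
- SSW = kX² − 13 × (kX/13)²
- F = (SSB/3) / (SSW/48). X² cancels, so the size of the change does not matter.

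| k | SSB / X² | SSW / X² | F(3,48) | p |
|---|---|---|---|---|
| 1 | 0.0577 | 0.9231 | 1.00 | 0.40 |
| 2 | 0.2308 | 1.6923 | 2.18 | 0.10 |
| 3 | 0.5192 | 2.3077 | 3.60 | 0.02 |

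The case k = 1 does not depend on the arm size. For total N and an affected arm of n, the limit for one extreme value is F = [(1/n − 1/N)/3] / [(1 − 1/n)/(N − 4)]. With N = 4n, both numerator and denominator equal 1/(4n), so F = 1 exactly. With arms of 13, 13, 13 and 14 and the patient in an arm of 13, F = 1.03 and p = 0.39; in the arm of 14, F = 0.93 and p = 0.44.

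**Step 4: with background variation.** 2,000 simulated trials per setting, with arms of 13, 13, 13 and 14, assumed normal values with mean 25 and SD 5, 10 or 20, and one patient in an arm of 13 set to the value shown.

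| Patient's value | Trials with p < 0.05 | Median p | Arm mean | Arm median | Arm SD | Arm maximum |
|---|---|---|---|---|---|---|
| 900 | 0% at every SD | 0.39 | 92 | 26 to 27 | 243 | 900 |
| 200 | 0% to 2.8% | 0.40 to 0.45 | 38 | 25 to 27 | 49 to 52 | 200 |

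The p-value misses the patient. The maximum column shows the patient. A count of subjects would show 1/13, or 7.7%.

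**The case against.** The strongest reply is that the plan shows individual cases in several ways. The median, minimum and maximum are planned, and all values, including unscheduled ones, are listed. Laboratory results, vital signs and examination findings judged clinically significant or noteworthy become AEs, and SAP 8.1 tabulates AEs by number and percentage of subjects, by severity and by relationship. SAP 8.3 gives counts and percentages for physical examination and vital signs. The protocol gives no unit of count for the endpoint. SAP 2.3 states no safety hypothesis, so no decision depends on the laboratory p-values. Appendix 5 may list a shift table.

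Most of this stands, and it rules out several stronger readings:

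- A reader might infer that the whole endpoint cannot be produced. That is true only of X-rays and ECG; data for the other components are collected.
- A reader might infer that laboratory values are shown only as means, or that one severely affected patient would be invisible. SAP 5.5 and the listings contradict both. Only the p-value is blind to such a patient.
- A reader might infer that the SAP dropped X-rays and ECG on its own. The synopsis and the protocol's Endpoints text already omit them, so the conflict lies within the protocol.
- A reader might infer that the trial will claim X-ray and ECG safety. No display covers either, so this is a risk created by the hypothesis wording and not a planned claim.

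The reply does not close the gap. A maximum says neither how many patients were affected nor whether the change mattered clinically. It also leaves out anything found only at an unscheduled visit, because SAP 8.2 keeps those values out of tables and figures. AE summaries by reported term have no laboratory category in the SAP text, and the protocol lists AEs as a separate endpoint. Listings do not compare arms.

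**Conclusion.** The point holds in this limited form. X-rays and ECG cannot be delivered as endpoint components, and the conflicting protocol passages must be reconciled. Urinalysis is planned but not collected; that leaves an empty display and causes no bias.

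For laboratory values, the SAP text has no arm-level display matching the endpoint, and its only inferential result cannot flag a single patient. With four arms of 13, one extreme patient gives p of about 0.40 whatever the size of the change, two in the same arm give 0.10, and three are needed for 0.02.

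These figures assume roughly equal arms and an effect confined to one arm. The two- and three-patient figures also assume equal changes in those patients that are large relative to background variation. The simulated mean and SD are assumptions, but the limiting one-patient result does not depend on them. The absence of a count or shift table is a statement about the SAP text without Appendix 5.

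This affects the reporting of a secondary safety endpoint. It does not affect the primary analysis.

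**What to change.** 1. In SAP 8.2, add a table of the number and percentage of subjects per arm with at least one laboratory change that the investigator flagged as clinically significant. The flag is already marked on each report and recorded as an AE.
2. Add shift tables by arm from baseline (as defined in SAP 5.2) to the worst post-baseline value. Include unscheduled values, with a matching exception to the SAP 8.2 sentence that excludes them from tables.
3. Label any laboratory ANOVA p-values that are kept as descriptive, and state that they are not evidence of safety.
4. Reconcile the Study Endpoints section and the two safety hypotheses with the synopsis, Table 2, the statistical Endpoints text and SAP 2.1, so that no X-ray or ECG conclusion is drawn without data.
5. Remove urinalysis from SAP 8.2.
6. If Appendix 5 already lists the tables in items 1 and 2, refer to them in SAP 8.2 as the displays for this endpoint.

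The cost is two tables from data that the protocol already collects, plus wording. If the investigator's flag is not held as a database variable, it would have to be derived from the AE records. If X-rays and ECG are removed, the stated safety scope becomes slightly narrower.
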